12.1.1 Randomization

Not applicable.

12.2 Interim analyses

Patient characteristics will be summarized using proportions for categorical variables, means and standard deviations for continuous variables (median and inter-quartile rages for variables that exhibit skewness). Adverse events and qualifying DLT will be tabulated by cohort, site and severity. Proportions of these patients in each response category will be tabulated; the combined proportion in categories CR, CRi, PR, SD will be computed along with an exact 95% confidence interval. Duration of response progression-free survival and overall survival will be computed from start of induction therapy and summarized with Kaplan-Meier estimates.

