Forty patients have been enrolled in the study with median age of 49 yrs (range 19-71). Baseline characteristics include 6 patients (15%) with secondary AML, 4 (10%) with prior transplant, 24 (60%) with intermediate and 10 (25%) with poor risk cytogenetics. Thirty-six patients (90%) received Plerixafor + MEC as their 1st salvage regimen for relapsed disease with 21 (53%) having a CR1 duration of < 12 months and 9 patients (6%) for primary refractory disease. The remaining four patients (10%) received the regimen as their 2nd salvage regimen. Three dose levels of Plerixafor: 80, 160 and 240 µg/kg were tested in the phase I dose escalation. In the phase II, a total of 34 patients have been treated at the 240 µg/kg dose level. Common grade ≥3 adverse events consisted primarily of cytopenias and infections. No evidence of hyperleukocytosis or significant delays in neutrophil recovery (ANC >500/mm3, median 27d, range 21-37) or platelet recovery (plt >50k/mm3, median 26d, range 20-40d) were observed. Of the 32 patients evaluable for response at the 240 µg/kg dose level, a complete remission (CR+CRi) has been achieved in 50% of patients (CR=13, CRi=3) which compares favorably to historical CR rates of 25-35%. Treatment failure was due to persistent disease in 14 patients (44%) and early death due to complications from infection in 2 patients (6%). One year KM estimate of overall survival is currently 56%.

Correlative studies demonstrated that Plerixafor mobilizes AML blasts (mean 2.5-fold increase, range 0.9-7.3 fold) into the peripheral circulation peaking at 6-8 hours after administration. FISH performed in patients with informative cytogenetic abnormalities indicates that mobilization occurs equally in both non-leukemic and leukemic populations. Higher baseline surface CXCR4 expression correlated with increased mobilization of AML blasts (Pearson's r=0.53, p=0.023) into the PB at 6 hrs post-Plerixafor. It was concluded that Plerixafor can be safely administered in combination with cytotoxic chemotherapy in patients with AML [67].

A phase I study is also being conducted to determine the MTD and safety of Plerixafor when combined with cytarabine and daunorubicin (7+3 regimen) for newly diagnosed adult AML [68]. Plerixafor was given as a 30-min IV infusion, 4–5 hours before daunorubicin beginning on day 2 and repeated every day until day 7. Dose levels were from 240, 320, and 400

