3.1 Inclusion Criteria

- 3.1.1 Patients must have tissue confirmation of high grade (WHO Grade IV) glioma including but not limited to glioblastoma, gliosarcoma, glioblastoma with oligodendroglial features, glioblastoma with PNET features.
- 3.1.2 The patient must have post-operative contrast enhanced imaging (CT or MRI) unless only biopsy performed (in which case post-operative imaging is not routinely obtained. In these patients, the preoperative study will serve as baseline.
- 3.1.3 Patient should have surgery (biopsy, partial resection or gross total resection) and no additional anti-cancer therapy except the chemoradiation as specified in the protocol.
- 3.1.4 For those patients in which steroids are clinically indicated, there must be a stable or decreasing dose of steroid medication for \geq one week prior to the start of infusion.
- 3.1.5 Patients must be between the ages of 18 and 75 years old.
- 3.1.6 Patients must have Karnofsky Performance score ≥ 60 .
- 3.1.7 Adequate organ function is needed at time of screening visit including:
 - 1. ANC ≥ 1500
 - 2. Platelets > 100.000 ml
 - 3. Serum Creatinine ≤ 1.5mg/dl; Cr clearance should be > 50 mL/min
 - 4. AST and ALT \leq 3 times the upper limit of normal

Page 21 of 52

- 5. Serum potassium, magnesium and calcium within normal limits (supplementation to maintain normal electrolyte levels is acceptable)
- 6. If female of childbearing potential, negative pregnancy test
- 3.1.8 The patient or his/her legal representative must have the ability to understand and willingness to sign a written informed consent document.
- 3.1.9 Patient agrees to use an effective method of contraception (hormonal or two barrier methods) while on study and for at least 3 months following the Plerixafor infusion

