10.2.3 Measurement Methods

Endpoint will be measured based on the RANO criteria, using both clinical examinations and MRIs with and without contrast.

Complete Response (CR): Requires all of the following:

- Complete disappearance of all enhancing measurable and non-measurable disease
- Stable or improved non-enhancing (T2/FLAIR) lesions
- No new lesions
- Off corticosteroids (or on physiologic replacement dose)
- Stable or improved clinical status

Partial Response (PR): Requires all of the following:

- ≥ 50% decrease compared with baseline in the sum of the products of the diameter (SPD) of measurable enhancing target lesions
- No progression of non-target disease (enhancing and non-enhancing (T2/FLAIR) lesions)
- No new lesions
- Corticosteroid dose stable or decreased
- Stable or improved clinical status

Stable Disease (SD): Requires all of the following:

- Does not qualify for CR, PR or PD
- Stable non-enhancing (T2/FLAIR) lesions
- Corticosteroid dose not increased > 50%
- Stable or improved clinical status

Progressive Disease (PD): Requires any of the following

- \geq 25% increase in the SPD of measurable enhancing target lesions plus >5 mm absolute increase in the sum of the longest diameters (SLD) of target lesions compared to the best response after initiation of therapy
- Clear progression of enhancing non-target disease
- Significant increase in T2/FLAIR non-enhancing disease not caused by co-morbid events (eg radiation therapy, demyelination, ischemic injury, infection, seizures, post-operative changes or other treatment effects)

- Any new lesions
- Clear clinical deterioration not attributable to other causes apart from the tumor (eg, seizures, medication adverse effects, complications of therapy, cerebrovascular events, infections etc)
- Increasing steroid doses alone do not constitute PD.

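### Section 12.2 starts duration of response, PFS and OS at an induction therapy that this trial does not have, and counts time before response as response

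*Combined protocol and SAP*

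**What the plan says.** Section 12.2 (Interim analyses) plans three things for efficacy. First, "Proportions of these patients in each response category will be tabulated". Second, "the combined proportion in categories CR, CRi, PR, SD will be computed along with an exact 95% confidence interval". Third, "Duration of response progression-free survival and overall survival will be computed from start of induction therapy and summarized with Kaplan-Meier estimates".

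Section 10.2.3 sets the response criteria: "Endpoint will be measured based on the RANO criteria, using both clinical examinations and MRIs with and without contrast". It defines CR, PR, SD and PD and no other category.

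The treatment in section 2.4 is six weeks of irradiation with temozolomide, Plerixafor from seven days before irradiation ends, then adjuvant temozolomide. None of these is named induction.

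Elsewhere, six-month PFS runs from the start of irradiation (1.1), the first day of radiation (time frame in section 10) or the start of chemoradiation (10.2.2). Section 10.2.1 instead evaluates patients six months after chemoradiation is completed.

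**The concern.** Section 12.2 is the only place that names an estimator for PFS and OS, and its time origin cannot be located in the treatment plan. The analyst would have to choose one. PFS stands in that sentence, and section 10.1 makes PFS at six months the Phase II primary objective, so the choice reaches beyond descriptive summaries.

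Duration of response has a second fault that any choice leaves in place. Counted from a treatment start, it includes the weeks before a response was seen. The error always lengthens the result, and it affects every responder.

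The response categories also need tidying. CRi is not in 10.2.3, and the combined proportion includes stable disease without being named as disease control.

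**Working it through.** The plan gives no response rate or duration for this analysis, so there is no figure to reproduce. The check is day arithmetic on the protocol's own schedule.

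Inputs:
- Irradiation lasts six weeks, taken as 42 days (2.4).
- Plerixafor Day 1 is 7 ± 3 days before irradiation ends, so 4 to 10 days before (section 4).
- The first scan after irradiation is 28 ± 7 days after it ends, so 21 to 35 days (section 4), or 35 ± 3 days, so 32 to 38 days (10.2.4). These two timings conflict.
- A further scan falls six months after the start of irradiation, ± 2 weeks (section 4).

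**Gap between the two readings of the origin.** Radiation start to Plerixafor Day 1 is 42 − 10 = 32 to 42 − 4 = 38 days.

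**Time before response included in its duration.** A response first documented on the first scan after irradiation carries:

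| Origin | Scan timing in section 4 | Scan timing in 10.2.4 |
|---|---|---|
| Radiation start | 42 + 21 = 63 to 42 + 35 = 77 days | 42 + 32 = 74 to 42 + 38 = 80 days |
| Plerixafor Day 1 | 21 + 4 = 25 to 35 + 10 = 45 days | 32 + 4 = 36 to 38 + 10 = 48 days |

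These are minimum amounts for the given scan date. A response first seen on a later scan carries more.

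**Six-month landmark.** With the origin at Plerixafor Day 1, six months falls 32 to 38 days after the nominal scan, which is 32 − 14 = 18 to 38 − 14 = 24 days after its window closes. With the origin at completion of chemoradiation (10.2.1), it falls 42 − 14 = 28 days after the window closes.

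**CRi.** No patient can be assigned CRi under 10.2.3. An assumed 12 of 20 stays at 60.0% (exact 95% interval 36.1% to 80.9%) with or without it.

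**Patients without measurable disease (assumed counts).**
- Combined proportion: take 12 of 20 (60%) and exclude 4 patients without measurable disease. If 0, 2 or 4 of those were free of progression, the result is 12/16 = 75.0%, 10/16 = 62.5% or 8/16 = 50.0%. The direction is not fixed.
- CR plus PR: take 4 responders, all with measurable disease. The rate is 4/20 = 20.0% (5.7% to 43.7%) over all patients. Excluding a share of 20%, 40% or 50% gives 4/16 = 25.0%, 4/12 = 33.3% or 4/10 = 40.0% (12.2% to 73.8%).

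**The case against.** The strongest reply is that section 12.2 is descriptive. Response and its duration are not objectives in 1.1 or 10.1, and they play no part in the decision rule in 12.4, 12.5.2 and 12.7. Six-month PFS is given an origin elsewhere, so a careful analyst would use the start of radiation. This stands for response and its duration. It stands only in part for PFS: the decision rule states no origin for its six months, 10.2.1 disagrees with 1.1 and 10.2.2, and 12.3 is marked not applicable.

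A reader might go further and infer that the response proportion and its interval will be wrong. The documents do not support that. CRi is an empty category. The combined figure includes SD, so scoring a resected patient CR rather than SD leaves the numerator unchanged. Patients without measurable disease can validly be SD or PD, so keeping them in is not in itself an error.

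A reader might also infer that surgery will be counted as complete response, because 3.1.3 admits gross total resection. But the criterion is "Complete disappearance of all enhancing measurable and non-measurable disease", and disappearance presupposes something present at baseline. Criterion 3.1.2 requires post-operative imaging and uses the pre-operative scan as baseline only after biopsy alone. Against a post-operative baseline without enhancement, nothing has disappeared on treatment. The text states no explicit rule for such patients, so the point is open rather than shown.

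Finally, CRi and induction may suggest wording carried over from a leukaemia plan. CRi otherwise occurs only in the leukaemia background of section 2.5, for example "a complete remission (CR+CRi) has been achieved in 50% of patients". The inference is reasonable, but the documents do not say so.

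**Conclusion.** The time origin in section 12.2 is undefined for this trial and should be corrected. The two natural readings differ by 32 to 38 days for PFS and OS, and the wording conflicts with the start-of-radiation or chemoradiation origin in 1.1, 10 and 10.2.2. Section 10.2.1 is a separate conflict on the same endpoint.

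Duration of response is overstated under either reading, by at least about 9 to 11 weeks from radiation start or about 4 to 7 weeks from Plerixafor Day 1. The stray CRi has no numerical effect. For the combined proportion, the gap is one of naming. For separate CR and PR proportions, the missing measurable-disease set affects interpretation.

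The figures assume a 42-day irradiation course, scans inside their stated windows, no response documented before the first scan after irradiation, and that the 12.2 sentence lists three separate endpoints although no comma follows the first. The percentages rest on assumed counts. The practical weight is moderate: only the PFS origin touches the Phase II primary endpoint.

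**What to change.** Rewrite the efficacy part of section 12.2 and align the related sections:
- Measure duration of response from first documented CR or PR to PD or death.
- Measure PFS and OS from the first day of radiation, as 1.1 already does for six-month PFS, and correct 10.2.1 to match.
- Delete CRi.
- Label the CR, PR and SD proportion as disease control and keep its exact interval.
- Where CR and PR proportions are shown separately, also report them in patients with measurable enhancing disease on the baseline scan. Restricting the combined proportion to those patients would be a preference, not a correction.
- Reconcile the first-scan timing in section 4 with that in 10.2.4.

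The analysis changes are wording only and need no new data. The price is shorter reported durations and a smaller denominator for the separate CR and PR figures.

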12.3 Descriptive Statistics and Exploratory Data Analysis

Not applicable.

12.4 Primary Analysis

For the Phase II component, it is expected that no more than 50% of patients will have stable disease at 6 months (defined as stable MRI and clinical status, including being on a stable dose of steroids and not on bevacizumab). We will therefore consider this regimen of interest if significantly more than 50% of patients achieve this benchmark.

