	for newly diagnosed glioblastoma GBM.
STUDY PHASE	I/II
INDICATION	Newly diagnosed glioblastoma
INVESTIGATIONAL PRODUCT OR PROCEDURE	Continuous infusion of Plerixafor
PRIMARY OBJECTIVE(S)	Efficacy as measured by progression free survival at 6 months
SECONDARY OBJECTIVE(S)	Safety of the continuous infusion of Plerixafor subsequent to irradiation
TREATMENT SUMMARY	200 micrograms per kilogram per day for four weeks, in second patient will increase to target dose of 400 micrograms per kilogram per day for four weeks, and continue treatment of subsequent patients at the target dose if tolerated.
SAMPLE SIZE	29 patients
STATISTICAL CONSIDERATIONS	Dose-escalation study with planned dose levels using the modified toxicity probability interval (mTPI). For efficacy, a greater than 50% PFS at 6 mos. PFS will be considered a positive signal and warrant further study.

SCHEMA

*Infusion will last for either two or four weeks with Phase I dose determined per the adjustment rules described in section 12.1; Phase II dose and duration determined in the Phase I

LIST OF ABBREVIATIONS AND DEFINITION OF TERMS

ABW Actual Body Weight ADL Activities of daily living AE Adverse event CBC Complete blood count CMAX Maximum concentration of drug CNS Central nervous system CRF Case report/Record form CR Complete response CTCAE Common Terminology Criteria for Adverse Ever DLT Dose Limiting Toxicity DSMB Data Safety Monitoring Board ECG Electrocardiogram GBM Glioblastoma GI Gastrointestinal HIV Human Immunodeficiency Virus IBW Ideal Body Weight IRB Institutional Review Board IV Intravenous KPS Karnofsky Performance Score MTPI Modified Toxicity Probability Interval OS Overall survival PLT Platelet PD Progressive disease PFS Progression free survival	ts
AE Adverse event CBC Complete blood count CMAX Maximum concentration of drug CNS Central nervous system CRF Case report/Record form CR Complete response CTCAE Common Terminology Criteria for Adverse Ever DLT Dose Limiting Toxicity DSMB Data Safety Monitoring Board ECG Electrocardiogram GBM Glioblastoma GI Gastrointestinal HIV Human Immunodeficiency Virus IBW Ideal Body Weight IRB Institutional Review Board IV Intravenous KPS Karnofsky Performance Score MTPI Modified Toxicity Probability Interval OS Overall survival PLT Platelet PD Progressive disease PFS Progression free survival	ts

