1. OBJECTIVES

1.1. Primary Objectives

- To assess the safety of using continuous infusion Plerixafor beginning one week prior to the end of concurrent chemotherapy with Temozolomide and radiation therapy in patients with newly diagnosed GBM.
- To assess the efficacy of Plerixafor as measured by progression free survival at 6 months (PFS6) from the start of irradiation.

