10.2.2 Measurement Definition

This endpoint of PFS6 months post start of chemoradiation will be assessed using RANO criteria.

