12.5 Secondary Analysis

Our Primary objective in the Phase II component is to assess progression free survival at 6 months.

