12.7 Criteria for future studies

This is a pilot study with the expectation that no more than 50% of patients will have stable disease at 6 months (defined as stable MRI and clinical status, including being on a stable dose of steroids and not on bevacizumab). We will therefore consider this regimen of interest if significantly more than 50% of patients achieve this benchmark and would move further to future studies should this benchmark be reached.

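### The Phase II objective is RANO PFS6, but the success rule is worded as a stable-disease benchmark that scores some patients differently, and the threshold and the start of the six-month clock also conflict

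*Combined protocol and SAP*

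**What the plan says.** **Objective.** Section 1.1 reads "To assess the efficacy of Plerixafor as measured by progression free survival at 6 months (PFS6) from the start of irradiation". Section 10.1 agrees, and 12.5 repeats it: "Our Primary objective in the Phase II component is to assess progression free survival at 6 months". Section 10.2.2 sets the method: "This endpoint of PFS6 months post start of chemoradiation will be assessed using RANO criteria".

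**RANO as written in 10.2.3.** Under progressive disease: "Increasing steroid doses alone do not constitute PD". Stable disease is the category that "Does not qualify for CR, PR or PD", and it tolerates a corticosteroid increase of up to 50%.

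**Decision rule.** Sections 12.4, 12.5.2 and 12.7 expect at most half of patients to have stable disease at six months, "defined as stable MRI and clinical status, including being on a stable dose of steroids and not on bevacizumab". They continue: "We will therefore consider this regimen of interest if significantly more than 50% of patients achieve this benchmark". Section 12.7 makes this the condition for going on to further studies.

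**Synopsis.** "For efficacy, a greater than 50% PFS at 6 mos. PFS will be considered a positive signal and warrant further study". It mentions neither significance, steroids nor bevacizumab.

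**Clock.** Sections 1.1, 10 and 10.2.2 count from the start of radiation or chemoradiation, and the six-month MRI in sections 4 and 10.2.4 is timed the same way. Section 10.2.1 counts six months from the completion of chemoradiation.

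**The concern.** A single-arm trial of 20 patients ends in one count compared with one cut-off. Here the objective and the rule describe the countable patient differently, the synopsis and section 12 set different thresholds, and 10.2.1 moves the assessment date. Two analysts following the text could reach different verdicts from the same data. The trial is open-label and the investigators read the scans (10.2.5), so the choice between readings should not remain open once outcomes are visible. It is also unclear which outcome the 50% reference rate describes: 12.6.3 cites a historical control rate without saying how success was defined there.

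**Working it through.** There is no plan figure to reproduce. Section 12.6.2 says the sample size gives enough power but states no alpha, power or alternative rate.

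**1. Scoring the same patient both ways**

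| Patient | RANO PFS6 (10.2.3) | Benchmark (12.4, 12.5.2, 12.7) |
|---|---|---|
| Steroid dose raised by up to 50%, no PD | Success, and can still be SD | Fails if a stable dose is read literally; no reference time is given |
| Steroid dose raised by more than 50%, no PD | Success, though no longer SD | Fails |
| CR or PR | Success | Unclear: not SD under 10.2.3. Exclusion is probably unintended, since 12.2 pools CR, PR and SD |
| Bevacizumab started without PD | Success | Fails; should be uncommon given 3.2.1 and 4.1 |
| PD earlier, stable at month 6 | Failure | Unclear: could pass if read as status at month 6 |

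**2. Threshold.** Inputs: n = 20 (12.5.1) and a reference rate of 50% (12.4). Let X be the number of successes, X ~ Bin(20, 0.5).

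- Synopsis, more than 50%: X ≥ 11. P(X ≥ 11) = 0.412.
- Section 12, significantly more than 50%: P(X ≥ 15) = 0.0207 and P(X ≥ 14) = 0.0577. Alpha is not stated. The cut-off is 15 at a one-sided 0.05 or 0.025, and 14 at a one-sided 0.10.

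With a cut-off of 15, any count from 11 to 14 is positive under the synopsis and negative under section 12, even if every patient is scored identically. At a true 50% that happens with probability 0.412 − 0.021 = 0.391.

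**3. Clock.** Radiation lasts six weeks, with 42 days of concurrent temozolomide (2.4). The two origins therefore differ by 42 days. The six-month MRI window in section 4 is ± 2 weeks, or 14 days, so one scan cannot serve both.

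**4. How often the verdict could turn (illustration).** Let p be the true PFS6 rate and f the share of PFS6 successes that fail the benchmark. Assume no PFS6 failure passes the benchmark, and apply the cut-off of 15 to both. Then X ~ Bin(20, p) and the benchmark count is Y ~ Bin(20, p(1 − f)) with Y ≤ X, so

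P(verdicts differ) = P(X ≥ 15) − P(Y ≥ 15).

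| p | f = 2% | f = 5% | f = 10% |
|---|---|---|---|
| 75% | 0.617 − 0.556 = 0.061 | 0.617 − 0.465 = 0.152 | 0.617 − 0.325 = 0.292 |
| 60% | 0.126 − 0.105 = 0.021 | 0.126 − 0.078 = 0.047 | 0.126 − 0.046 = 0.080 |
| 50% | 0.0207 − 0.0166 = 0.004 | 0.0207 − 0.0118 = 0.009 | 0.0207 − 0.0064 = 0.014 |

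At p = 75%, P(X = 15) = 0.202. In about one trial in five, PFS6 lands exactly on the cut-off, where one patient scored differently changes the conclusion.

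**The case against.** The best defence is structural. Section 12.5 names PFS6 as the Phase II objective, and 12.5.2, its analysis plan, gives the benchmark. The same wording stands as the primary analysis in 12.4 and as the criterion in 12.7. The natural reading is that the benchmark is the working form of PFS6. A reader might infer that the plan holds two rival endpoints and gives no guidance between them; that goes too far. What remains is that the protocol never states the equivalence, and that if it is intended, the steroid condition contradicts 10.2.3.

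The steroid conflict can also be narrowed. If a stable dose is shorthand for the RANO SD condition, only increases above 50% without PD are scored differently. That is plausible, but the text does not say it.

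A reader might also infer that misclassification in both directions would make verdicts diverge often even when the two success rates are equal. The documents do not support this. To hold both rates at 75% while a share f of successes is lost, the share g of PFS6 failures scored as stable must satisfy 0.25g = 0.75f. With f = 5% that gives g = 15%; with f = 20%, g = 60%. Patients who have died cannot be stable, 4.2 lists progression as a reason for removal, and 10.2.4 ends study scans at progression. I rely on no such scenario.

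Finally, the values of f have no source in the documents, and 12.7 calls this a pilot study. Both points stand and limit the weight of the illustration.

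**Conclusion.** The concern holds as an inconsistency in definition, threshold and time origin. It should be fixed, but it does not invalidate the design. The contradictions between 10.2.3 and 12.4, between the synopsis and section 12, and between 10.2.1 and 1.1 are in the text and need no assumption.

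The size does rest on assumptions: a one-sided alpha of 0.05 or 0.025, misclassification in one direction only, and f of 2% to 10%. On these, verdicts differ in 6% to 29% of trials at a true PFS6 of 75% and in 0.4% to 1.4% at 50%. It might be inferred that the ambiguity between the two definitions inflates type I error. With one cut-off applied to both, it does not: at a true PFS6 of 50% the benchmark passes no more often than PFS6 does. The 41% false-positive rate belongs to the literal synopsis threshold alone.

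**What to change.** Before data are seen, put one binary success definition, one time origin (first day of radiation) and one cut-off with its alpha into the synopsis, 10.2.1, 12.4, 12.5.2 and 12.7. Wording consistent with the stated objective would be:

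*Success is being alive and free of RANO progression (10.2.3) at the six-month MRI, counted from the first day of radiation. CR, PR, SD and a steroid increase without PD count as success. PD, death or no evaluable assessment counts as not a success. The denominator is all treated Phase II patients.*

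Report the stable-steroid, no-bevacizumab version as a sensitivity analysis. Give a reference time for the steroid dose, and state how responders and an early progressor who is stable at month 6 are scored. If the sponsor prefers that version as primary, say so and report RANO PFS6 alongside. Confirm which definition the 50% describes and restate the null if it differs. All of this concerns scoring only, not when steroids or bevacizumab may be given.

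The cost is wording, one extra analysis, and recording steroid dose and bevacizumab use at the MRI visits already planned up to month 6. That recording is needed because section 4 follows concomitant medication only to 30 days after the infusion. On the four-week schedule this is day 42 − 7 + 28 + 30 = 93 from the start of radiation, against about day 183 for month 6. Counting unevaluable patients as failures makes the estimate slightly conservative: one missed scan can turn 15 of 20 into 14 of 20.

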12.5.1 Analysis Population

20 additional patients will be enrolled in the Phase II component of this study for determination of efficacy.

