12.5.2 Analysis Plan

For the Phase II component, it is expected that no more than 50% of patients will have stable disease at 6 months (defined as stable MRI and clinical status, including being on a stable dose of steroids and not on bevacizumab). We will therefore consider this regimen of interest if significantly more than 50% of patients achieve this benchmark.

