12.6.2 Sample size justification

In collaboration with our statistician, it was determined that our sample size of 29 total patients would substantiate enough power to reach our points of analyses.

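### The Phase II go/no-go rule is written in two conflicting ways, on two different events, and neither section gives a test, alpha or cut-off

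*Combined protocol and SAP*

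**What the plan says.** The synopsis, under Statistical Considerations, says: "For efficacy, a greater than 50% PFS at 6 mos. PFS will be considered a positive signal and warrant further study". It sets no significance requirement.

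Section 12.4 says: "We will therefore consider this regimen of interest if significantly more than 50% of patients achieve this benchmark". Section 12.5.2 repeats this, and section 12.7 ties it to the same decision: "significantly more than 50% of patients achieve this benchmark and would move further to future studies should this benchmark be reached". The benchmark in all three is stable disease at 6 months, "defined as stable MRI and clinical status, including being on a stable dose of steroids and not on bevacizumab".

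The objective in section 1.1 is PFS6. Section 10.2.2 says how it is measured: "This endpoint of PFS6 months post start of chemoradiation will be assessed using RANO criteria". Section 10.2.3 adds: "Increasing steroid doses alone do not constitute PD".

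On sample size, section 12.5.1 says "20 additional patients will be enrolled in the Phase II component of this study for determination of efficacy", and section 12.6.2 says "it was determined that our sample size of 29 total patients would substantiate enough power to reach our points of analyses". Section 12.6.3 refers to a historical control rate but gives no alternative rate.

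**The concern.** This is the only efficacy decision in Phase II, and the plan leaves both of its parts open.

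- **Threshold.** A point estimate just over 50% satisfies the synopsis. Section 12 asks for statistical significance but does not define it.
- **Event.** A patient who is progression-free by RANO but on a raised steroid dose counts as a success for PFS6 and a failure for the section 12 benchmark. Read literally, a benchmark of stable disease also leaves it unclear whether complete and partial responders count.

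The study is single-arm and open-label, and its own investigators read the MRIs (sections 2.4 and 10.2.5). With the rule unsettled, the same data can be reported as positive or negative, and the choice can be made after the results are known.

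**Working it through.** **Inputs.** n = 20 (section 12.5.1); reference rate p0 = 0.50 (section 12.4). Alpha, sidedness, test and target rate are not stated, so ranges are assumed below.

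**The plan's own figure.** The claim that 29 patients give sufficient power cannot be reproduced, because alpha, power and the target rate p1 are missing. Two sets of inputs can be back-fitted:
- n = 20: one-sided 0.025, 80% power, p1 = 0.80 (exact binomial, at least 15/20, power 0.804).
- n = 29: one-sided 0.025, 80% power, p1 = 0.75, by normal approximation: [(1.960 × 0.500 + 0.842 × 0.433)/0.25]² = 28.9, so 29. The exact calculation gives 30.

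Neither set is in the documents.

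**Operating characteristics.** For cut-off k, P(go) = P(X ≥ k) with X ~ Binomial(20, p).

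| Rule | p=0.50 | 0.60 | 0.65 | 0.70 | 0.75 | 0.80 |
|---|---|---|---|---|---|---|
| ≥11 (synopsis, more than 50%) | 0.412 | 0.755 | 0.878 | 0.952 | 0.986 | 0.997 |
| ≥14 | 0.058 | 0.250 | 0.417 | 0.608 | 0.786 | 0.913 |
| ≥15 | 0.021 | 0.126 | 0.245 | 0.416 | 0.617 | 0.804 |

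Below the reference rate, the synopsis rule still gives a go with probability 0.249 at p = 0.45 and 0.128 at p = 0.40.

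**Cut-off implied by significance.** P(X ≥ k | 0.50) is 0.132, 0.058, 0.021 and 0.006 for k = 13, 14, 15 and 16. An exact test at one-sided 0.05, one-sided 0.025 or two-sided 0.05 therefore needs 15. One-sided 0.10 needs 14, 0.15 needs 13 and 0.01 needs 16. An uncorrected score test at one-sided 0.05 needs 14: z = 0.20/√(0.25/20) = 1.79, p = 0.037.

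**Probability that the two rules disagree**, P(11 ≤ X ≤ k − 1), taking the same event for both:

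| Section 12 cut-off | Conflict zone | p=0.50 | 0.60 | 0.70 |
|---|---|---|---|---|
| 13 | 11–12 | 0.280 | 0.339 | 0.180 |
| 14 | 11–13 | 0.354 | 0.505 | 0.344 |
| 15 | 11–14 | 0.391 | 0.630 | 0.536 |
| 16 | 11–15 | 0.406 | 0.704 | 0.715 |

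A conflict zone exists under every choice tried.

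**Effect of the event mismatch.** The documents give no figure, so this is illustration only. Let q be the share of progression-free patients who miss the section 12 benchmark because of steroid dose or bevacizumab. With true PFS6 of 0.75, the benchmark rate is 0.75 × (1 − q):
- q = 0: rate 0.750, P(X ≥ 15) = 0.617
- q = 0.05: rate 0.713, 0.465
- q = 0.10: rate 0.675, 0.325
- q = 0.20: rate 0.600, 0.126

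**Sensitivity with all 29 patients.** More than 50% means at least 15/29, with type I error 0.50. One-sided 0.05 needs at least 20/29, actual alpha 0.031. The conflict remains.

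**The case against.** The strongest reply is that the synopsis is shorthand: it names the rate to beat, and section 12 gives the standard of evidence. On that reading the 41% figure describes a rule nobody meant to use. Even so, the operative rule is then section 12, which has no test, alpha or cut-off and counts a different event from the stated objective.

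Section 12.2 does specify an exact 95% confidence interval, the nearest thing to an error level. It applies to the combined CR, CRi, PR and SD proportion, sits under interim analyses, and is not linked to the decision. If it were used, the lower Clopper-Pearson limit is 45.7% for 14/20 and 50.9% for 15/20, so 15 successes would be needed and the synopsis would still disagree.

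The event gap is narrower than it first looks. Section 10.2.3 limits steroid increases to 50% within RANO stable disease, section 3.2.1 excludes prior or concurrent bevacizumab, and section 4.1 bars other systemic cancer therapy on study. This stands, but it does not close the gap: a raised steroid dose alone is still not progression under section 10.2.3, while it fails the section 12 benchmark.

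Section 12.7 calls this a pilot study, which supports a lenient alpha. It does not support leaving alpha unstated, since the same section sets the criterion for moving on.

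**Conclusion.** The concern holds, and the rule is wrong as written. The synopsis and section 12 give contradictory criteria for one decision, on different events, and the section 12 criterion cannot be applied without choices the plan does not make. Taken literally, the synopsis rule has a false-positive rate of 41% at a true rate of exactly 50%, lower below that. Under an exact test at one-sided 0.05 or 0.025, section 12 needs 15/20, and 80% power is reached only at a true rate of about 80%.

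The 41% follows from n = 20 and the synopsis wording. The section 12 cut-off, its power and the size of the conflict zone rest on an assumed test and alpha; other choices move the top of the zone between 12 and 15 successes without removing it. The power losses from the event mismatch rest on assumed shares and carry little weight beyond showing direction.

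**What to change.** Put one rule and one named endpoint in the synopsis and sections 12.4, 12.5.2 and 12.7, and delete the bare more-than-50% criterion. Example text:

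> The regimen is of interest if at least 15 of the 20 Phase II patients are alive and progression-free by RANO at 6 months from the start of irradiation (exact one-sided binomial test against 50%, nominal alpha 0.05, actual 2.1%). The exact 95% confidence interval will be reported.

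Another alpha is acceptable if it and its cut-off are fixed before data review. For example, 14/20 has actual alpha 5.8% and power of 61%, 79% and 91% at true rates of 70%, 75% and 80%.

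Report the stable-MRI, steroid and bevacizumab benchmark as a supportive proportion. If the sponsor prefers it as the decision endpoint, name it in section 1.1 and the synopsis instead, and say whether responders count. State how patients without a 6-month assessment are counted among the 20. Align section 10.2.1, which times PFS6 from completion of chemoradiation, with sections 1.1 and 10.2.2.

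In section 12.6.2 keep 29 as the total (9 plus 20), say that the efficacy test uses 20, and replace the general statement about power with figures for the chosen rule (for 15/20: 42%, 62% and 80% at 70%, 75% and 80%).

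The cost is protocol wording only, with no added patients. The stated power becomes explicit and less favourable, and under the example a positive call needs 15 successes instead of 11.
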